8.3.2 Form

Etoposide Injection USP is available in 100 mg(5ml) and 250 mg(12.5ml) sterile, multiple dose vials. The pH of the clear, colorless to pale yellow solution is 3 to 4. Each ml contains 20 mg Etoposide, 2 mg anhydrous citric acid, 30 mg benzyl alcohol, 80 mg polysorbate, 650 mg polyethylene glycol, and 30.5 percent (v/v) dehydrated alcohol.

8.3.3 Storage and Stability

Unopened vials of Etoposide Injection USP are stable for 24 months at room temperature. Vials diluted as recommended to a concentration of 0.2 or 0.4 mg/ml are stable for 96 and 24 hours, respectively, at room temperature under normal room fluorescent light in both glass and plastic containers.

8.3.4 Compatibility

Because specific compatibility data is not available, etoposide should not be mixed in the same infusion with other drugs.

CONFIDENTIAL

This document is confidential. Do not disclose or use except as authorized.

8.3.5 Handling

Procedures for proper handling and disposal should follow institutional guidelines. If Etoposide solution contacts the skin or mucosa, immediately and thoroughly wash the skin with soap and water and flush the mucosa with water.

8.3.6 Availability

Etoposide is commercially available and will not be provided for this study. It is supplied at 100mg/5ml and 250 mg/12.5 multiple dose vials.

8.3.7 Preparation

Etoposide Injection USP must be diluted prior to use with either 5% Dextrose Injection or 0.9% Sodium Chloride Injection, to give a final concentration of 0.2 to 0.4 mg/ml or per institutional standard. If solutions are prepared at concentrations above 0.4 mg/ml, precipitation may occur.

8.3.8 Administration

Hypotension following rapid intravenous administration has been reported; hence, it is recommended that the Etoposide solution be administered over a 30-60 minute period. A longer duration of administration may be used if the volume of fluid to be infused is a concern. Etoposide should not be given by rapid intravenous injection. The bag of etoposide should be inspected prior to administration and held if the solution is cloudy or precipitated drug is observed.

8.3.9 Ordering

Etoposide is commercially available. It will be ordered and supplied per institutional guidelines.

8.3.10 Accountability

Etoposide accountability will be handled via institutional chemotherapy policies.

8.3.11 Destruction and Return

N/A or handled via institutional chemotherapy policies.

8.4 Cytarabine

8.4.1 Description

Cytarabine (1-beta-D-arabinofuranosylcytosine) is a synthetic antineoplastic agent. The exact mechanism of action for cytarabine is unknown. It is thought that the drug is an antimetabolite, interfering with the synthesis of deoxyribonucleic acid (DNA). The inhibition of the conversion of cytidine to deoxycytidine is the presumed primary site of action. Cytarabine may be incorporated into DNA and RNA as in vitro chromosome breaks have been associated with the

CONFIDENTIAL

This document is confidential. Do not disclose or use except as authorized.

drug, and the clinical effects are limited to tissues with a high rate of cellular proliferation. Alternatively, cytarabine may have a differentiating role rather than an antimitotic effect as the mechanism of action. Cytarabine reportedly also has immunosuppressive activity. Two important properties of cytarabine include:

- A relatively unique synergistic effect with other classes of drugs including alkylating agents, thiopurines, and anthracycline antibiotics.
- Clinical effectiveness that is significantly affected by the schedule of administration. Cytarabine is effective for refractory leukemia and the addition of anthracyclines may enhance this effect.

8.4.2 Form

Cytarabine (Cytosar-U, Cytosine Arabinoside, Ara-C) for Injection, USP, is a sterile lyophilized material for reconstitution. It is available in multi-dose vials containing 100 mg, 500 mg, 1 g or 2 g sterile cytarabine. Cytarabine is commercially available and will not be provided for this study.

8.4.3 Storage and Stability

Cytarabine lyophilized powder should be stored at 150 to 300 C. Solutions reconstituted with Bacteriostatic Water for Injection with Benzyl Alcohol to 0.945% weight/volume may be stored at 15⁰ to 30⁰ C for up to 48 hours. The pH of the reconstituted solution is about 5. Solutions with a slight haze should be discarded. Solutions reconstituted with a preservative should be used immediately. Undiluted vials should be stored at room temperature. Reconstituted solutions are stable for 7 days at room temperature.

8.4.4 Compatibility

For intravenous cytarabine administration, cytarabine lyophilized powder should be reconstituted with Bacteriostatic Water for Injection with Benzyl Alcohol 0.945% weight/volume.

8.4.5 Handling

Cytarabine is manufactured by the Upjohn Company in Kalamazoo, MI, USA. Cytarabine is commercially available. Procedures for proper handling and disposal should follow institutional guidelines.

8.4.6 Availability

Cytarabine is commercially available and will not be provided for this study.

8.4.7 Preparation

Cytarabine should be reconstituted according to institutional standard; recommendations for reconstitution in Bacteriostatic Water for Injection with Benzyl Alcohol 0.945% weight/volume

CONFIDENTIAL

This document is confidential. Do not disclose or use except as authorized.

as a diluent as follows are provided below:

Vial lyophilized dose (mg)	Bacteriostatic Water for Injection with Benzyl Alcohol 0.945% (ml)	Final Cytarabine Concentration (mg/ml)
100	5	50
500	10	50
1000	10	100
2000	20	100

8.4.8 Administration

Cytarabine is administered intravenously, over approximately one hour. Cytarabine injection may induce hyperuricemia secondary to rapid lysis of leukemia cells. Periodic checks of bone marrow, liver and kidney functions should be performed in patients receiving cytarabine.

8.4.9 Ordering

Cytarabine is commercially available. It will be ordered and supplied per institutional guidelines.

8.4.10 Accountability

Cytarabine accountability will be handled via institutional chemotherapy policies.

8.4.11 Destruction and Return

N/A or handled via institutional chemotherapy policies.

9. BIOMARKER, CORRELATIVE, AND SPECIAL STUDIES

Correlative studies are optional. Patients who consent will have a purple top tube sent as standard of care for NGS molecular testing according to site SOC (e.g., Rapid Heme Panel, Heme SNaPshot assay) testing at the time of study entry, and subsequent bone marrows as clinically indicated. Missed samples due to weekends, holidays, insufficient volume or patient refusal will not be considered violations. Additional DNA will be stored for future testing, in the event of new genetic mutations.

9.1 Laboratory Correlative Studies

CORRELATIVE STUDY 1: Understanding the leukemia genetics of relapsed and refractory AML.

Acute myeloid leukemia (AML) is a disease characterized by the combinatorial action of multiple somatic mutations that lead to an arrest in normal hematopoietic differentiation and uncontrolled growth of immature bone marrow myeloid blasts (55,56). Advances in gene

CONFIDENTIAL

This document is confidential. Do not disclose or use except as authorized.

sequencing technology over the past decade have allowed for the identification of over 50 recurrent mutations in AML patients. Mutational testing of a limited number of genes is already considered an integral part of standard clinical practice. In myelodysplasia, a related myeloid disease, the finding of isolated deletion of 5q is an approved indication for the use of lenalidomide (57). Individual mutations can be associated with sensitivity to specific therapies and the development of resistance. For instance, mutations in *TP53* along with loss of chromosome 5q have been demonstrated to predict a poor response to treatment with lenalidomide (58). Recent work has also demonstrated that MDS clonal structure is dynamic during treatment with lenalidomide as some initially dominant clones disappear and founder clones tend to become dominant over time (59,60). Understanding these changes and how they relate to treatment response is an important next step in finding predictive markers to identify appropriate patients for selected therapies. In order to address these issues in this study of salvage chemotherapy combined with lenalidomide we plan to sequence recurrently mutated genes in myeloid malignancies using standard sequencing panels available at the institutions involved in the trial, such as the Heme SNaPshot assay available at Massachusetts General Hospital, and the Rapid Heme Panel assay at the Brigham and Women's Hospital Center for Advanced Molecular Diagnostics (CAMD). Sequencing using one of these assays or a similar assay is recommended at clinical trial enrollment, and then on subsequent bone marrows as clinically indicated. This assay can be performed from a single purple top tube collected from a bone marrow aspirate or per local SOP.

9.1.1.1 Collection of Specimen(s)

Collection of these samples is optional but recommended. A purple top tube of bone marrow aspirate (or other appropriate tube based on the assay) will be collected from each consenting patient: at study enrollment; the day + 35 (+/- 3 days) bone marrow biopsy if indicated or at count recovery if sooner;); as well as at relapse, if this occurs. For this correlative, the baseline mutation testing may be performed at the time of relapse and may occur up to 2 months prior to enrollment as part of clinical care, provided that no intervening therapy has been given except hydroxyurea or 6MP. If it cannot be obtained off the bone marrow, a sample using leukemic blood will be adequate.

9.1.1.2 Handling and Shipping of Specimens

- Sequencing and any sample shipping will be performed locally according to standard of care at each local institution.

CORRELATIVE STUDY 2: Assessing lenalidomide function in AML.

In myelodysplasia, a related myeloid disease, the finding of isolated deletion of 5q is an approved indication for the use of lenalidomide. This sensitivity to lenalidomide is mediated through selective proteosomal degradation CSNK1A1, a haploinsufficient gene found in the commonly deleted region of 5q. Lenalidomide induces degradation by binding to the E3 ubiquitin ligase cereblon thus altering its affinity for some targets such as CSNK1A1 and leading to its ubiquitination and eventual degradation. In multiple myeloma, another disease in which lenalidomide is approved, the proteins targeted for degradation are IKZF1 and IKZF3, which are crucial B-cell transcription factors. In both diseases, the genes targeted by lenalidomide show

decreased protein levels but no alteration in the RNA level. Therefore, the only way to assess this function of lenalidomide is through direct measurement of protein levels. In multiple myeloma, sensitivity to lenalidomide has been associated with the protein levels of cereblon and its associated complex.

Understanding whether these previously identified targets are also degraded in AML and whether cereblon levels might predict response to lenalidomide is important for understanding its mechanism of action in AML. We have previously used mass spectrometry to measure the levels of cereblon and lenalidomide targets in cell lysates. We propose to collect samples before and after treatment with lenalidomide to measure the levels of target proteins.

Peripheral blood and bone marrow will be collected at the following time points:

- Study enrollment, prior to initiation of treatment: 5ml peripheral blood and 2ml bone marrow aspirate
- On day 4, prior to initiation of MEC chemotherapy, a 5ml peripheral blood sample will be collected. This may be obtained before or after the dose of lenalidomide that day.
- Day +35+- 3 days (or at count recovery if sooner): 5ml peripheral blood and 2ml bone marrow aspirate (at the time of marrow assessment)

This correlative study is recommended but optional. Study samples will be collected and processed according to local tissue banking protocols.

MGH: patient samples will be collected and stored using the local tissue bank prior to analysis.

BWH/DFCI: patient samples will be collected and stored using the local tissue bank prior to analysis.

BIDMC: patient samples will be collected and stored using the local tissue bank prior to analysis.

UVA: patient samples will be collected and stored using the local tissue bank prior to analysis.

CORRELATIVE STUDY 3: Assessing the impact of therapy on tumor-reactive T-cells

In the phase I study on Lenalidomide and MEC, we found that exposure to this chemotherapy combination results in the expansion of IFN- γ expressing T-cells when exposed to leukemia cell lysate from the time of relapse. Using leukemia cells collected at baseline, when T-cells from pre-treatment and then at the end of therapy are exposed to the leukemia cell lysate, we saw a significant increase in the number of reactive T-cells following MEC and Lenalidomide. At the peak following MEC and lenalidomide therapy, there was a mean 3.8-fold and 7.5-fold increase in the level of IFN- γ expressing CD4+ and CD8+ T cells in the peripheral blood, respectively, consistent with the expansion of tumor-reactive T-cells. We therefore propose an optional correlative study to collect bone marrow and peripheral blood samples at diagnosis and at response to further evaluate the development of a leukemia-specific T-cell response after exposure to leukemia cells.

Blood and bone marrow specimens should be collected in heparinized tubes (large green top

CONFIDENTIAL

This document is confidential. Do not disclose or use except as authorized.

tubes). We will plan to collect approximately 25ml (3 large green top tubes) of peripheral blood and 4 ml (one small green top tube) of BM aspirates. The green top tubes should be sent to the [name] lab and delivered at room temperature within a couple of hours from collection using standard local shipping methods. If samples are not delivered immediately after collection, samples should be placed on cold packs and shipped. Samples may be shipped Monday-Thursday.

- Tubes will be collected at the following time points: Study enrollment, prior to treatment initiation: 3 large heparinized green top tubes (~25ml) of peripheral blood and 1 small green top tube (4ml) of bone marrow aspirate
- Count recovery or day 35 marrow: 3 large heparinized green top tubes (~25ml) of peripheral blood and 1 small green top tube (4ml) of bone marrow aspirate

Samples should be sent to:

Attn: [name],
Beth Israel Deaconess Medical Center, Center for Life Sciences,
[REDACTED]
[REDACTED]

CORRELATIVE STUDY 4: Dynamic BH3 profiling to predict clinical response to lenalidomide and MEC chemotherapy.

[figure not shown]
Background: One mechanism by which lenalidomide combined with MEC chemotherapy may impact responses to chemotherapy is by activating pro-apoptotic signaling. Apoptosis is regulated by the BCL-2 family of proteins, which encompass a number of pro-apoptotic and anti-apoptotic proteins. This family of proteins is classified by structure and BCL-2 homology (BH) domains; a subset of the BCL-2 family, containing BH3-only proteins, have pro-apoptotic function. The magnitude of apoptotic response of a tumor after being exposed to proapoptotic peptides is a measure of how “primed” a cell is to respond to BH3, and is associated with response to treatment with standard cytotoxic chemotherapy (Vo T-T et al. Cell. 2012(151): 344). More recently, the [name] lab has developed a functional assay to profile BH3 response after cancer cells have been incubated with a specific chemotherapy, and have shown that this correlates with the response to these agents ([REDACTED]). In a previous study, lenalidomide was given prior to MEC chemotherapy for patients with AML, and baseline samples underwent dynamic BH3 profiling after exposure to lenalidomide (Figure below).

CONFIDENTIAL

[figure not shown]
This document is confidential. Do not disclose or use except as authorized.

Response to activator

Bim $0.1\mu\text{M}$ v response $0.5\mu\text{M}$ LEN

Unpaired t test	
P value	0.0002
P value summary	***
Significantly different (P < 0.05)?	Yes
One- or two-tailed P value?	Two-tailed

Area under the ROC curve	
Area	0.9762
Std. Error	0.03692
95% confidence interval	0.9038 to 1.049
P value	0.0043

BH3 profiling performed on pre-treatment leukemia samples after exposure to lenalidomide showed that there was a significant increase in priming in the samples from patients who subsequently achieved a complete remission compared to those who did not respond to therapy ($p=0.0002$), suggesting that dynamic BH3 profiling may be a way to predict which patients will most likely respond to this combination, and which patients may be better served by alternative therapies. We therefore propose an optional correlative study to collect bone marrow or leukemic blood samples at diagnosis to perform BH3 profiling and correlate with responses.

Blood and bone marrow samples will be collected during treatment and sent to the [name] lab for analysis. We will plan to collect samples at baseline (prior to starting chemotherapy, 5mL bone marrow aspirate and 10mL peripheral blood) and at day 3 of treatment (peripheral blood only, 10mL sample). Baseline samples should be collected Monday-Friday; if collected Friday, they should be collected in the morning to allow same day shipping. Samples collected on day 3 should be sent in a similar fashion; if day 3 lands on a Saturday samples should be sent on day 2 (Friday), while if day 3 is a Sunday, samples may be collected on the morning of day 4 prior to MEC administration. Samples may be collected and shipped directly to the [name] lab, or may be stored and sent in batches, per the local site preferences/capability.

1. If samples are to be shipped one at a time directly from the center treating the patient, a heparinized aspirate tube may be used, shipped on blue ice to maintain a 4 degree F temperature (not wet ice or dry ice) after wrapping the tube with a dry pad. Samples should reach the [name] lab within 24 hours, and it would help a lot if we had notice so we were prepared to get it.
2. Preferred: samples that are stored and shipped as a batch should be viable frozen (e.g., in 10% DMSO, 90% serum).

Samples should be sent to:
 Dana-Farber Cancer Institute
 Attn: [name]
 [REDACTED]

CONFIDENTIAL

This document is confidential. Do not disclose or use except as authorized.

[name]

If possible, as samples are being prepared, contact [name] at
[REDACTED]

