5.3 Agent Administration

Treatment will be administered on an inpatient basis. Expected toxicities and potential risks for mitoxantrone, etoposide, cytarabine, and lenalidomide are outlined in Toxicities and Dosing Delays/Dose Modification (section 6).

Administer chemotherapeutic agents according to institutional policies and procedures. Lenalidomide should be administered prior to MEC each day. During the administration of MEC, mitoxantrone will be administered first, followed by etoposide, followed by cytarabine.

General dosing guidelines for lenalidomide are provided below. Please refer to the dosage and

CONFIDENTIAL

This document is confidential. Do not disclose or use except as authorized.

administration schedule specified in the prescribing information.

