6. DOSING DELAYS/DOSE MODIFICATIONS

Any dose modifications or delays in the reinduction chemotherapy regimen of mitoxantrone, etoposide, and cytarabine should be per the treating physician and institutional practice, with approval from the overall PI (also please refer to section 6.3, table 5).

There may be two dose reductions in lenalidomide per patient. Reduction of lenalidomide dose may be modified as follows:

Table 3: Lenalidomide Dose Reductions	
Dose Level	Lenalidomide dose
1 (starting dose)	50 mg
-1	25mg
-2	10 mg

No Lenalidomide will be given after Day 10, even if there are missed doses.

Dose delays and modifications will be made as indicated in Table 4. The descriptions and grading scales found in the revised NCI Common Terminology Criteria for Adverse Events (CTCAE) version 4.03 will be utilized for dose delays and dose modifications. A copy of the CTCAE version 4.03 can be downloaded from the CTEP website http://ctep.cancer.gov/protocolDevelopment/electronic_applications/ctc.htm.

CONFIDENTIAL

This document is confidential. Do not disclose or use except as authorized.

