8.1.2.4 Metabolism and Excretion

The metabolic profile of lenalidomide in humans has not been studied. In healthy subjects and patients with MM or MDS, approximately 65% to 85% of the administered dose of lenalidomide is eliminated unchanged through urinary excretion. The process exceeds the glomerular filtration rate and therefore is partially or entirely active. Half-life of elimination is approximately 3 hours.

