² All patients will have bone marrow examined at count recovery or at Day +35 +/- 3 days. Patient will be off treatment if persistent leukemia or need for further treatment. Patients who have count recovery within one week of the Day 35 marrow do not need a repeat bone marrow. Patients who have not experienced count recovery by Day 45 will have marrow at Day 45+/-3 days regardless of counts. Patients may have additional bone marrows performed as clinically indicated.

³The day 4 peripheral blood research sample should be obtained prior to the initiation of MEC chemotherapy (may be obtained before or after lenalidomide on that day).

⁴ Toxicity will be assessed from the time of first dose of study treatment through 30 days past the last dose of study treatment.

⁵Molecular testing (correlative 1) may be performed at the time of disease relapse and within 2 months of study enrollment, provided no intervening systemic chemotherapy has been administered (excluding hydroxyurea or 6MP).

^bSamples for optional correlative 4 may be collected at baseline prior to chemotherapy, and on day 3 of treatment (or day 2 or 4 if on a weekend, but prior to MEC administration).

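### Correlative Study 2 allows its only on-lenalidomide blood draw on either side of the Day 4 dose, with no window and no recorded times

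*Combined protocol and SAP*

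**What the plan says.** Correlative Study 2, under Section 9.1, states its aim as: "We propose to collect samples before and after treatment with lenalidomide to measure the levels of target proteins". The readout is protein level by mass spectrometry, because the protocol explains that lenalidomide lowers the protein without changing the RNA. Two questions are posed: whether the known targets are degraded in AML, and whether cereblon level might predict response.

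There are three collection points:

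- **Enrollment:** blood and marrow, before any treatment.
- **Day 4:** blood only, before MEC starts.
- **Day +35 (± 3 days), or count recovery if sooner:** blood and marrow.

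On the Day 4 draw the text says: "This may be obtained before or after the dose of lenalidomide that day". Footnote 3 to Table 6 (Section 10.4) agrees: "may be obtained before or after lenalidomide on that day". Neither gives a dose-to-draw interval or asks for one to be recorded.

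Lenalidomide runs from Day 1 to Day 10, and Section 6 adds: "No Lenalidomide will be given after Day 10, even if there are missed doses". On the order of drugs within a day, Section 5.3 says: "Lenalidomide should be administered prior to MEC each day". The length of the gap between lenalidomide and MEC is not stated. Section 8.1.2.4 says: "Half-life of elimination is approximately 3 hours".

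**The concern.** Day 4 is the only point in Correlative Study 2 at which a patient is taking lenalidomide and has not yet received MEC. The last sample, at Day 35, comes 35 − 10 = 25 days after the final scheduled dose and after chemotherapy. The Day 3 blood belongs to Correlative Study 4, a different assay in a different laboratory. The degradation question therefore rests on the change from enrollment to Day 4.

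The protocol attributes degradation to lenalidomide binding cereblon, so time since the last dose is a plausible determinant of the protein level measured. If some patients are drawn about a day after the Day 3 dose and others shortly after the Day 4 dose, differences in timing can be mistaken for differences in biology. A null result in a pre-dose sample could also mean either no degradation or recovery since the previous dose. Four centers collect under local tissue-banking procedures. If their draw habits differ, which is an inference, timing would be confounded with site. Without recorded times, none of this can be adjusted for later.

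**Working it through.** The documents state no sample size, power or exposure figure for this study, so there is no plan figure to reproduce. The check uses the protocol's own pharmacokinetics.

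**Inputs.** Time to peak is 0.7 to 2.0 h, half-life is 2.8 to 6.1 h, decline is monophasic and no accumulation was observed (Sections 2.3.1 and 8.1.2.2, myeloma patients). Section 8.1.2.4 gives a half-life of about 3 h. Doses are taken at about the same time each day (Section 5.3.1), so the interval is nominally 24 h.

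**Consistency of the inputs.** Accumulation ratio = 1 / (1 − 2^(−24/t½)). This is 1.003 at 2.8 h, 1.004 at 3 h and 1.07 at 6.1 h, in line with the statement that no accumulation was seen.

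**Step 1: plasma exposure.** Trough/peak = 2^(−(24 − Tmax)/t½).

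| t½ (h) | Tmax (h) | Half-lives from peak to trough | Trough as % of peak | Fold difference |
|---|---|---|---|---|
| 2.8 | 0.7 | 23.3/2.8 = 8.32 | 0.31 | 320 |
| 2.8 | 2.0 | 22/2.8 = 7.86 | 0.43 | 232 |
| 3.0 | 0.7 | 23.3/3.0 = 7.77 | 0.46 | 218 |
| 3.0 | 2.0 | 22/3.0 = 7.33 | 0.62 | 161 |
| 6.1 | 0.7 | 23.3/6.1 = 3.82 | 7.1 | 14.1 |
| 6.1 | 2.0 | 22/6.1 = 3.61 | 8.2 | 12.2 |

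A one-compartment oral model was used as a cross-check, with the absorption rate solved from Tmax and three earlier daily doses. It gives 11- to 14-fold at 6.1 h, 121- to 207-fold at 3 h and 167- to 302-fold at 2.8 h, which is the same picture.

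The previous dose time matters too. A missed dose may be taken later the same day, until midnight. If the interval shrank to 12 h (an assumed value), the fraction left, 2^(−12/t½), would be 5.1% at 2.8 h, 6.3% at 3 h and 25.6% at 6.1 h.

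**Step 2: effect on the protein readout.** This step rests on assumption, because the documents give no recovery rate. Let w be the share of patients drawn pre-dose and r the fraction of the post-dose knockdown still present at trough. In units of the post-dose knockdown, mean measured knockdown = 1 − w(1 − r), and added between-patient SD = √(w(1 − w)) × (1 − r).

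| r | w = 0.25: mean / SD | w = 0.50: mean / SD | w = 0.75: mean / SD |
|---|---|---|---|
| 1 (full persistence) | 1.00 / 0 | 1.00 / 0 | 1.00 / 0 |
| 0.5 | 0.875 / 0.22 | 0.75 / 0.25 | 0.625 / 0.22 |
| 0 (no persistence) | 0.75 / 0.43 | 0.50 / 0.50 | 0.25 / 0.43 |

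**The case against.** The strongest reply is that the fold differences describe plasma drug, whereas the study measures protein. If the targets stay depleted for a day or more after a dose, a pre-dose and a post-dose draw give the same answer and nothing is lost. That stands: the first row of the second table is a real possibility, and the documents cannot rule it out. They also give no reason to assume it.

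Three stronger readings are tempting, and the documents do not support them:

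- **That every post-dose draw is near peak.** The protocol says only that lenalidomide comes before MEC. A sample taken minutes after the capsule would still be close to trough, so the trough-versus-peak contrast is the widest that the rule permits, not what will necessarily occur. Counting a full 24 h of decline from peak would give about 380-fold at 2.8 h (1/0.0026), but this ignores the stated time to peak.
- **That the study cannot answer its questions.** The cereblon-and-response question can use the enrollment sample, which Day 4 timing does not touch.
- **That the Day +35 sample is put forward as evidence of on-drug degradation.** The text makes no such claim for it.

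It is also fair to say that the stakes are low. The study is optional, the only correlative among the secondary objectives is genetic profiling, and Section 13 specifies no analysis of these proteins. The choice appears in two places and so looks deliberate. Treatment is inpatient, so dose and draw times might be recovered from records, although the protocol does not ask for them for this sample.

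**Conclusion.** The point holds as a cheap improvement of low stakes. The plan allows an avoidable source of between-patient variation in the one measurement that bears on degradation, and it does not secure the data needed to adjust for it. The 12- to 320-fold plasma range assumes daily dosing at 24 h, a draw exactly at trough or at peak, and half-lives and times to peak taken from myeloma patients. At the 6.1 h half-life, trough is still 7% to 8% of peak, so a pre-dose sample is low in drug but not clearly drug-free. The effect on measured knockdown runs from zero to a halving at an even split of draw times, and further if more patients are drawn pre-dose. Where it falls depends on recovery kinetics that the documents do not give. The primary endpoint of CR plus CRp is unaffected.

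**What to change.** In Correlative Study 2 and in Table 6 footnote 3:

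1. Set the Day 4 research draw to one consistent side of that day's lenalidomide dose. The assay laboratory should choose the side and the window from what it knows of protein recovery. Either side would standardize the sample, and the documents do not support a particular number of hours. The window must fit the existing lenalidomide and MEC schedule and must not change or delay treatment.
2. Record the times of the previous lenalidomide dose, the Day 4 dose (if already given) and the draw.
3. State that the analysis of change from baseline will use the dose-to-draw interval, as a covariate or a stratum.

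If the sponsor prefers to keep the flexibility, items 2 and 3 alone would still make the data interpretable. The cost is a small scheduling constraint on an optional blood draw and two or three extra recorded times. No tube, visit, dose or order of drugs changes.
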